### 4.32 Focus Group Study B

As of October 2018, the results of the initial focus groups (Focus Group Study A) have been used to create the interview guide being used during the exercise stress visit. The initial qualitative analysis of the collected data provides a description of post-exertional malaise in which there may be four key symptom concepts (cognitive difficulties, extreme fatigue, flu-like symptoms, and muscle pain/weakness) and a time course in which to expect the onset of PEM. The medical literature has a paucity of detailed qualitative studies about PEM in ME/CFS; there is currently only a single study of 19 persons. An expansion of the work performed in Focus Group Study A work has the potential to contribute to broader knowledge of PEM.

Focus group Study B will expand the scope of our focus group study activities. This expansion will include collecting more extensive demographic information, information about symptom severity, information about CPET experiences, and collection of medical records for diagnostic confirmation purposes. The purpose of this data collection would be to provide more extensive information about the similarities and differences of PEM in daily life compared with that occurring after CPET.

For Focus Group Study B, the investigative team will conduct up to 20 focus groups. Each group will contain between three to seven ME/CFS patients, with the maximum number of focus group study B participants being 140. Focus group participants will not be eligible to participant in the main study (Visit 1 phenotyping and Visit 2 exercise stress) but may participate in the Technical Development Substudy (TDS) and represent their own recruiting pool. NIH employees will not be eligible to participate in the focus groups. The focus groups will take place over the telephone to accommodate a nonmobile and geographically dispersed population.

Focus group participants will be persons with ME/CFS in the community willing to participate in telephone discussions with the investigative team to describe their experiences of PEM and provide medical records for diagnostic confirmation.

### Inclusion criteria for focus group B participants

- 1. Adult 18 years or older
- 2. Self-report of being diagnosed with ME/CFS in the community.
- 3. Self-report of having experienced post-exertional malaise.
- 4. Ability to speak, read, and understand English.
- 5. Able and willing to participate in focus group telephone call.

6. Willing to share their medical records with the investigative team for diagnostic confirmation.

### Exclusion criteria for focus group B participants

- 1. Participation in the phenotyping and exercise stress studies.
- 2. Decline to be audio-taped during the focus group.

Initially, participants will be recruited from persons who have contacted the investigative team about participating in any aspect of this protocol. These potential focus group participants will be contacted by phone and screened for inclusion/exclusion using Focus Group B Participation Checklist (Appendix 26.4). Potential focus group participants will be informed that focus group participation precludes participation in the phenotyping and exercise stress studies. The investigative team will contact interested individuals to answer any questions and address concerns, work with participants in completing paperwork to obtain pertinent medical records, and schedule times for obtaining telephone informed consent. The NIH will cover the costs of obtaining medical records. If recruitment goals are not met using the protocol's recruitment pool, a letter of invitation (Appendix 26.4) will be sent to community advocacy groups to be shared with their members and may posted on-line at NIH ME/CFS websites. Persons interested in participating in the focus group will contact the investigative team and undergo screening as detailed above. The investigative team may target specific under-represented ME/CFS sub-groups, such as minorities with ME/CFS, males with ME/CFS, persons aged 18-29 with ME/CFS, and bedbound ME/CFS participants.

Persons found to be eligible will be mailed a copy of the focus group consent form (Appendix 26.4). The individual will be instructed to read the consent form and be ready at the appointed date and time to review the consent document with an investigator authorized to obtain consent. Decision making capacity will be assessed and documented. If the subject is determined not to have decision making capacity, the telephone consent process will be halted, and the participant will be determined ineligible for participation in the focus group.

Potential participants with decision making capacity will be asked: "Do you agree to voluntarily participate in this study?" The consenting investigator will document the date and time oral consent was obtained on a consent procedure note. The participant will sign and date the consent form in the presence of a witness. The witness will also sign and date the consent form. The subject will be instructed to mail the consent form back to the site, where the investigator will sign and date the form. The investigator will then send a copy of the form with all signatures to the subject. The original consent document will be placed in the research chart.

After the investigative team receives the informed consent form, the focus group participant will be contacted to schedule a focus group teleconference time and to coordinate the collection of medical records.

The purpose of the focus groups is to gather information to collect information about the experience of PEM in daily life and the experience of PEM after CPET. Each focus group will be a joint discussion in which all of the scheduled participants will participate together. Overview guides for the Focus Group Study B discussions have been developed (Appendix 26.4). [name] will moderate the focus groups. Persons who decline to be audio-taped will not be included in the focus groups. Focus groups will be rescheduled if less than three participants make themselves available for the telephone call.

Recruitment for the focus groups will seek to categorize participants by level of disability: persons with symptoms that have maintained their activity level, persons whose activity has been limited by symptoms, and persons fully disabled and/or housebound from their symptoms.

Data collected during focus groups will consist of audio recordings which will be sent to a professional service for transcription via a secure website. Data, recordings, and transcriptions will be stored in locked cabinets. Transcriptions will NOT contain any identifying information and will be labeled with a number only. Basic demographics will be collected on all focus group participants but will not be associated with the corresponding transcriptions and will be kept secure and confidential. The demographic and descriptive information that will be collected can be reviewed in Focus Group B Participation Checklist (Appendix 26.4). Contact information that contains personally identifying information for focus group participants will be kept on file for five years after the conclusion of the study.

The risks of focus group participation include potential breach of confidentiality and emotional feelings that may arise with discussing personal feelings in a group setting. There is no direct benefit from focus group participation. Focus group participants will not be compensated for their participation.

An in-depth qualitative analysis process, thematic analysis, will be used to systematically code and categorize the textual data. Two investigators will read over the transcripts several times to allow immersion into the data, and then agreed upon a preliminary

categorical structure or "coding scheme." They then independently "coded" all of the transcripts (i.e. the textual data), which involved identifying salient categories, collating those categories into overarching themes, and assigning names to the themes. After the two researchers independently coded all the textual data, codes will be compared to identify disagreements and meetings will be conducted to discuss coding differences atlength and reach consensus. A qualitative software package (such as MAXQDA) will be used to highlight text within the transcripts and create categories and sub-categories electronically.

### 4.4 Technical Development Sub-Study

During the Exercise Stress Visit (Visit 2), participants will undergo a sequence of transcranial magnetic stimulation (TMS), functional magnetic resonance imaging (fMRI), and electroencephalography (EEG). An overview of those neurological measurements are described in full in Sections 4.6.15 and 4.6.16 below. To refine these techniques, up to 10 healthy volunteers and up to 10 ME/CFS participants will be enrolled on an outpatient basis for the purpose of having the TMS, fMRI, and EEG measures streamlined. This sub-study will be used to refine the timing and sequencing of different measurements and tasks, to ensure that the various equipment involved works harmoniously with each other, provide the investigative team experience in synchronizing these different measurements and using them in ME/CFS volunteers.

4.4.1 Inclusion criteria for all participants in the technical development substudy

- 1. Adult participants aged 18-60 years at the time of enrollment.
- 2. Ability to speak, read, and understand English.
- 3. Willing and able to complete all study procedures
- 4. Right-handed
- 5. Able to provide informed consent.

4.4.2 Exclusion criteria for the technical development sub-study

- 1. Active infection (e.g. influenza, urinary tract infection) by history, physical examination. These participants may be re-evaluated after the acute infection resolves.
- 2. Current or past psychotic disorder including depression with psychosis, bipolar disorder, and schizophrenia
- 3. Current DSM-5-defined major depression disorder, generalized anxiety disorder, post-traumatic stress disorder, panic disorder, or obsessive-compulsive disorder unless managed for more than six months with a stable treatment regimen
- 4. Current substance use as determined during medical history and by urine toxicology. Marijuana use will not be considered an exclusion.
- 5. Current suicidal ideation as determined during medical history
- 6. Women who are pregnant,
- 7. Current or previous malignancy. Certain dermatologic malignancies (e.g. basal cell carcinoma) will be allowed. A history of malignancy that have

fully resolved with resection only (i.e. no chemotherapy, radiation therapy, or immunotherapy) will be allowed.

- 8. Current immunologic disorder (e.g. Type 1 diabetes, rheumatoid arthritis)
- 9. Current or previous long term immune suppressive or immunomodulatory therapy.
- 10. Any medical condition that would exclude from participation in the phenotyping and exercise stress visits (eg, congestive heart failure, coronary artery disease, chronic obstructive pulmonary disease, severe osteoarthritis, poorly controlled asthma) or make the study procedures risky for the participant (e.g. seizure disorder).
- 11. Participation in a clinical protocol (e.g. centrally-acting drug intervention study) which includes an intervention that may affect the results of the technical development sub-study.
- 12. Clinically significant claustrophobia
- 13. Not willing to allow for research samples to be shared with other researchers.
- 14. Employees or staff at NIH that are directly supervised by the primary investigator or associate investigators.

4.4.3 Additional inclusion criteria for ME/CFS participants in the technical development study

1. Licensed Independent Practitioner documentation of ME/CFS

4.4.4 Additional exclusion criteria for ME/CFS participants in the technical development study

- 1. Significant neurological disorder (e.g. neurodegenerative disorder, stroke, epilepsy).
- 2. ME/CFS disease severity that makes it impossible for the volunteer to leave the home or requires inpatient treatment.
- 3. Current treatment for underlying illness that may cause fatigue such as thyroid dysfunction, hepatitis, or other systemic diseases.

Right-handed healthy volunteers interested in participating in the protocol may also be invited to participate in the technical development sub-study. Qualified healthy volunteers may participate in both the sub-study and the phenotyping/exercise stress visits. For participants interested in both parts of the study, participation in the technical development sub-study must occur prior to the phenotyping visit (Visit 1). Healthy volunteers participating in the technical development sub-study will complete a specific informed consent form; participants in both parts of the study will need to complete two informed consent forms.

Participation in the technical development sub-study will be made available to righthanded ME/CFS patients with that inquire about participation in the protocol, are generally healthy, have no medical issues that would increase risk of having TMS and MRI, but are found not meet the protocol's strict criteria for post-infectious causation or symptom duration. PI-ME/CFS participants that enroll in the phenotyping and exercise stress visits will be ineligible for participating in the technical development sub-study.

All participants in the technical development sub-study will have a detailed history and physical examination and urine toxicology. ME/CFS diagnostic status will be determined using the Fukuda, Canadian Consensus Criteria, and the Institute of Medicine Diagnostic Criteria. Participants will need to meet at least one of these criteria. Women of childbearing age will have urine pregnancy testing performed within 24 hours of fMRI and/or TMS. For participants undergoing fMRI that have not had a clinical MRI scan at the NIH in the past year, the investigative team will collect the clinical MRI sequences prior to fMRI experiments. It is anticipated that all measurements in the technical development sub-study, including TMS, MRI, and EEG, can be completed during 1-3 outpatient visits.

The timing of each test in the electrophysiology and fMRI sequences is crucial for obtaining precise images and determining how the different measured parameters change following the physical and mental fatiguing tasks. Once a task begins, it will trigger a chain of operations. For the TMS procedure, this includes applying single and double TMS pulses at precise intervals during the electrophysiology sessions. For the fMRI procedure, this includes synchronizing the markers of the fMRI sequence with both the EEG and the behavioral performance during the fatiguing tasks. Normal differences between individuals' task adherence can introduce a jitter in synchronization, ranging from differential ability to perform a task at different time points to missed trials. This sub-study will train the team to troubleshoot missed trials in real-time, identify potential weak points in the chain of events that need special attention, and adapt the procedure accordingly. The sub-study will also identify the average and minimum number of block/task that healthy volunteers and ME/CFS patients yield, which will help the investigators determine the minimum set of recordings that are required to extract the complete amount of information desired.

Participants will also complete questionnaires as part of the technical development substudy. These include: NIH-BFI. MFI-20, MASQ, SF-36, PROMIS, BDI-II, BAI, and PDS. These questionnaires are described in detail in Sections 4.5.5 and 4.6.6.

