#### **Précis:**

*Objective* The primary objective is to explore the clinical and biological phenotypes of post-infectious myalgic encephalomyelitis/chronic fatigue syndrome (PI-ME/CFS). The secondary objective is to explore the pathophysiology of fatigue and post-exertional malaise (PEM).

*Study population* Up to 346 persons will be enrolled as part of this protocol. Up to 150 persons aged 18-60 will be part of 3 study groups: 50 ME/CFS patients whose fatigue began after an infection, 50 non-fatigued participants with a documented history of a full recovery from a COVID-19 infection, and 50 healthy volunteers. The study has a target of completing all study procedures on 20 enrolled participants in each group. Up to an additional 176 persons reporting a community diagnosis of ME/CFS will be enrolled into focus groups to discuss the experience of post-exertional malaise. Up to an additional 10 ME/CFS patients may be enrolled to refine the protocol's electrophysiological and neuroimaging techniques.

*Design* This is a single-center, exploratory, cross-sectional study of PI-ME/CFS. Participants will have a *phenotyping visit*, which will encompass a 2-5 day long inpatient admission at the NIH Clinical Center. Case status for ME/CFS participants will be determined after the phenotyping visit by a *case adjudication* process utilizing an expert physician committee and published guidelines. Adjudicated participants meeting inclusion criteria will be invited back to participate in an *exercise stress visit*, which will encompass a 5-10 day long inpatient admission. Detailed subjective and objective measurements and biological specimens will be serially collected before and up to 96 hours after a peak exercise test capable of inducing post-exertional malaise during this visit. All procedures will be completed on all three study groups to allow for optimal inter-group comparisons.

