Healthy volunteers in the technical development sub-study may also participate in the phenotyping and exercise stress visits. Participation in the technical development substudy will be made available to documented ME/CFS patients that inquire about participation in the protocol and would otherwise be eligible to participate but do not meet study criteria for post-infectious causation or for having symptoms for less than 5 years. ME/CFS patients that participate in the technical development sub-study are excluded from participation in the phenotyping and exercise stress visits but may participate in focus groups.

The phenotyping visit (Visit 1) is designed to clearly define and document the characteristics of the study populations as well as collect biological samples. Eligible participants will undergo a set of research measurements and procedures. The results from the phenotyping visit will enable cross-sectional comparisons between the three study groups.

The exercise stress visit (Visit 2) will occur up to 12 months after the phenotyping visit. The exercise stress visit is designed around an exercise intervention designed to evoke the characteristic post-exercise malaise of PI-ME/CFS. All participants will undergo careful clinical description and a variety of biological measurements before, during, and after peak exercise testing. Qualitative interviews, subjective reporting on questionnaires, physiological measurements, neuroimaging, and biological samples will be serially collected. Only HV and PI-ME/CFS participants will be invited to participate in the exercise stress visit. These measurements will enable cross-sectional comparisons between these two study groups as well as comparisons between pre- and post-exercise state within and between study groups.

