## 4.6.17 : fMRI

fMRI will be completed during the exercise stress visit and will occur on two separate days, once before and once after the exercise challenge. The following imaging paradigm will be utilized: The subject will lie in the scanner operating a dynamometer to measure the force generated by the muscles of the distal upper limb in a first phase of the scan, and a button box for answering a cognitive test in the second phase of the scan. A structured set of imaging tasks are planned. An optional MRI-compatible electroencephalogram cap may be installed on subject's head before installing the subject in the MRI scanner in order to monitor the cortical activity during fMRI scanning and to allow the measurement of the cortico-muscular coupling during the muscular and cognitive fatiguing exercises. This may add about 30 min to the setup time.

Each scanning session will begin with a localizing image, an anatomical scan, and resting-state BOLD acquisition (20 minutes).

A test of cognitive fatigue will be performed within the MRI environment before the muscular fatigue test. In this study, there will be a sequence of two-choice reaction times. The correct choice will be based on a simple cognitive operation and the difficulty of the operation will not change over the series. Cognitive fatigue will be deemed present if the reaction time increases over the sequence. The test will continue for 10 minutes. fMRI will be done for 10 minutes, and the task analyzed as an event related design. The time between reaction time trials will be jittered, so that the MR signal can be extracted. The behavioral data and the MR data will be related parametrically. Another resting BOLD acquisition will be performed after the cognitive task. Even if no significant learning is expected related to the task, the subjects will get some training on the task prior to the MRI study so the novelty and/or any amount of learning will be further minimized. Subjective appraisals of cognitive fatigue will be measured at intervals during the cognitive fatigue task (20 minutes).

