If the overall multivariate test is significant, we will follow up with several post-hoc tests. Specifically, we will first conduct multivariate tests to compare the adjudicated PI-ME/CFS group (i.e. participants determined to have PI-ME/CFS by the protocol's adjudication process) vs the other two control groups, and the PI-ME/CFS group vs each of the two control groups. These analyses will initially performed using only HV and COVID-19 HV participants meeting all inclusion and exclusion criteria. As noted above, for analyses that are statistically significant, the analysis will be repeated using all HV and COVID-19 HV participants that did not report substantial clinical fatigue to determine if the results remain statistically significant when less stringent inclusion/exclusion criteria are applied.

Second, univariate ANOVA will be used for both cross-sectional measurements and pre and post exercise measurements separately to identify differences among groups. A
similar univariate analysis will be conducted for the measurements of change from pre- to post exercise using the univariate ANOVA.

Additionally, descriptive statistics will be used to characterize the entire group of ME/CFS participants that completed the phenotyping evaluation regardless of adjudication. Comparisons will be made between the adjudicated PI-ME/CFS group and the phenotyping ME/CFS group. If there is no significant difference between the above two groups, it is not necessary to compare a ME/CFS group to our two control groups. Where statistically appropriate, the ANOVA methods described above will be used to compare the ME/CFS group with the two control groups.

Statistical approaches such as chi-square tests and multinomial logistic regression models will be used to examine the group differences for categorical outcomes.

A level of significance is set at 0.05. Multiple comparison test procedures such as Bonferroni and Dunnett's methods will be used to examine the differences in each outcome measure among groups.

The primary MRI imaging aim is to test whether PI-ME/CFS group has significantly different connectivity patterns compared to the HV control group.

To this end, functional MRI measures will be taken at three conditions: 1) performing a force task, 2) performing a cognitive task, to define a network of interest, and 3) at rest to compute functional connectivity. At each condition, fMRI will be measured at two time points: pre exercise (preEx) and post exercise (postEx).

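### Healthy volunteers, but not patients, may do the fMRI/TMS/EEG sub-study before the main study, and the analysis plan does not account for this prior exposure

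*Combined protocol and SAP*

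**What the plan says.** The technical development sub-study (section 4.4) exists to refine the TMS, fMRI and EEG measures of the exercise stress visit, including the physical and mental fatiguing tasks. It provides that "up to 10 healthy volunteers and up to 10 ME/CFS participants will be enrolled on an outpatient basis", and section 4.4.4 expects all measurements to fit into one to three outpatient visits.

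The entry rules differ by group:

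- **Healthy volunteers (HVs).** Section 4.4.4: "Qualified healthy volunteers may participate in both the sub-study and the phenotyping/exercise stress visits". Anyone doing both must complete the sub-study before Visit 1 and signs two consent forms.
- **Patients.** Section 4.1: "ME/CFS patients that participate in the technical development sub-study are excluded from participation in the phenotyping and exercise stress visits". Section 4.4.4 gives the same bar from the other side: "PI-ME/CFS participants that enroll in the phenotyping and exercise stress visits will be ineligible for participating in the technical development sub-study".

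The sample target is in the Précis: "The study has a target of completing all study procedures on 20 enrolled participants in each group". Section 12.1 sets the imaging contrast: "The primary MRI imaging aim is to test whether PI-ME/CFS group has significantly different connectivity patterns compared to the HV control group". Connectivity is computed at rest, in regions defined from the force and cognitive tasks. The connectivity model has group status and fatigue scores as predictors; the task-activity model adds behaviour and fatigue scales as covariates. Nothing in section 12 identifies, adjusts for or sets aside HVs who came through the sub-study.

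Section 4.6.17 shows that the sponsor has practice in mind: subjects are trained on the cognitive task before scanning "so the novelty and/or any amount of learning will be further minimized". No such training is described for the force task.

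**The concern.** Earlier experience of the scanner, the reaction-time task, the sustained-contraction task or TMS could change reaction time, task activation, apprehension and time to fatigue. If only controls can bring the sub-study experience with them, part of an observed PI-ME/CFS versus HV difference may reflect familiarity rather than disease. It could also hide a real difference, depending on its direction.

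The outcomes are not equally exposed. Task activation and task performance are affected directly, as is TMS where it is done. Resting connectivity can be affected only indirectly: through regions chosen from task data, through resting scans acquired after a task in the same session, or through familiarity with the scanner.

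The study is exploratory, but its output is carried forward. Markers that differ between groups go on to ROC analysis against the HV group (section 12.1), and effect sizes feed the design of later studies (sections 4.1 and 12.2). An unrecorded group artefact would travel with them.

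**Working it through.** **The plan's own figures.** The documents give no figure for overlap or practice. The nearest is the fMRI justification in section 12.2 (12 subjects for 80% power at 0.05, supporting 20 per group). It states no effect size, SD, sidedness or design, so it cannot be reproduced; the present point does not depend on it.

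**Inputs.**
- Maximum HVs in the sub-study: 10 (section 4.4).
- Target completers per group: 20 (Précis); enrolment ceiling per group: 50 (section 12.2).
- Main-study patients with sub-study exposure: 0 (sections 4.1 and 4.4.4).
- Practice effect p: not in the documents. Assumed 0.2 to 0.5 SD, for illustration only.

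**Step 1: share of HVs exposed.** f = 10/20 = 50% at most among target completers, or 10/50 = 20% at the ceiling. The true value may be anything down to 0%. For patients it is 0%.

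**Step 2: spurious difference with no true group difference.** Bias = f × p. At f = 0.5 this is 0.5 × 0.2 = 0.10 SD to 0.5 × 0.5 = 0.25 SD.

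**Step 3: false-positive rate.** For a two-sided 5% comparison of two means, 20 per group, SD held at 1: SE = √(2/20) = 0.316, and rate = Φ(bias/SE − 1.96) + Φ(−bias/SE − 1.96). For bias 0.25: 0.25/0.316 = 0.79, so Φ(−1.17) + Φ(−2.75) = 0.121 + 0.003 = 0.124.

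| HVs exposed | p (SD, assumed) | Bias (SD) | False-positive rate |
|---|---|---|---|
| 10/20 | 0.2 | 0.10 | 6.2% |
| 10/20 | 0.5 | 0.25 | 12.4% |
| 5/20 | 0.2 | 0.05 | 5.3% |
| 5/20 | 0.5 | 0.125 | 6.8% |
| 2/20 | 0.2 | 0.02 | 5.0% |
| 2/20 | 0.5 | 0.05 | 5.3% |

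**Step 4: likely amount of sub-study exposure.** The payment schedule in section 24 lists $10 per hour for up to 8 hours, $40 for fMRI, $40 for TMS, $20 for EEG and $10 for questionnaires: 80 + 40 + 40 + 20 + 10 = $190, the stated maximum for completing both tasks. That suggests one fMRI and one TMS session per person.

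**Step 5: precision if sub-study HVs are left out.** The difference detectable with 80% power is (1.960 + 0.842) × √(1/n₁ + 1/n₂).
- 20 vs 20: 2.802 × 0.316 = 0.89 SD.
- 10 vs 20 (worst case): 2.802 × 0.387 = 1.09 SD. Power at 0.886 SD (the unrounded 0.89) is Φ(0.886/0.387 − 1.96) = about 63%, against 80%.

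**The case against.** The strongest reply is that patients are not barred from practice, only from the sub-study. Section 5.1.7 offers a single fMRI session, identical to that of Visit 2, at Visit 1 or as an extra outpatient visit. The schedule in section 25.1 for PI-ME/CFS and HV participants lists fMRI and TMS as optional before Visit 2. A reader might infer that patients always arrive unpractised; the documents do not support that. What remains is that this route is open to HVs as well, so it does not offset the additional one. It also requires medication washout where needed. Section 13.8 expects a majority of participants to be taking such medication, while section 3.3.4 excludes HVs who use it, so the route is plausibly harder for patients.

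A reader might also infer up to three rehearsal sessions from the one to three visits in section 4.4.4. Those visits cover all sub-study measurements, and the payments point to one session of each kind.

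Other mitigations carry weight:
- All subjects are trained on the cognitive task, its difficulty is constant and no significant learning is expected (section 4.6.17). Equal training narrows a gap in experience but does not cancel it, and it is not described for the force task.
- Behaviour as a covariate may absorb part of a performance difference in the task-activity model.
- A shift that is the same at both scans cancels in pre-to-post change, but not in cross-sectional contrasts.
- Visit 2 may follow Visit 1 by up to 12 months, so practice may fade.

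Finally, each session begins with resting BOLD before any task, and connectivity is the primary MRI outcome. To conclude that task practice is confounded with group in that comparison would therefore go too far.

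**Conclusion.** The asymmetry is explicit and section 12.1 does not deal with it. The supported conclusion is that differential prior exposure could partly confound the PI-ME/CFS versus HV comparisons, directly for task and TMS outcomes and only indirectly for resting connectivity. The documents do not show that it has done so: overlap is permitted, not required, and its actual extent is not stated.

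The size rests on two unknowns. At the maximum overlap, with an assumed practice effect of 0.2 to 0.5 SD, the false-positive rate is about 6% to 12%; at a quarter of HVs exposed it is about 5.3% to 6.8%, and at 2 of 20 it is close to nominal. The assumed effects have no source in the documents, least of all for resting connectivity, and the calculation gives no credit for the mitigations.

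This justifies a cheap improvement. It does not justify excluding sub-study HVs from the primary comparison by default or barring them from enrolment. Nor does the right-handedness rule of the sub-study (section 4.4.1) add anything: it applies to both of its arms, and no consequence for the main comparison is shown.

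**What to change.** In sections 4.4 and 12.1:

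1. Record for every PI-ME/CFS and HV participant any fMRI, TMS or task-EEG session before Visit 2, whether in the sub-study or as an optional procedure.
2. Prespecify a sensitivity analysis that reports each PI-ME/CFS versus HV comparison of fMRI, TMS and task-EEG outcomes with and without sub-study HVs.
3. Treat a finding as robust only if it persists without them. Judge this on the estimate and its confidence interval as well as the p-value, because the restricted analysis is less precise.

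The cost is a little more analysis and, in the restricted analysis only, a worst case of 10 HVs against 20 patients. Overlap can be identified from the two consent forms, so the change also works for data already collected, including the interim analysis described in section 12.3. If no HV did both parts, one sentence saying so closes the matter.
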